The current IMDs guidelines are cautious about the recommendations on the use of CGM and its clinical practice application in nutritional improvements or modifications (15–17). Rossi et al. have recently proposed indications for CGM monitoring and CGM outcome parameters in patients with hepatic GSDs (14). Peeks et al. also indicated outcome parameters for hepatic GSDs (13).

Worth et al. have recently analyzed the state of art of the evidence for the use of CGM in non-diabetic children with hypoglycemia (9). Some suggestions for qualified CGM use have been provided, but a focus on patients' perspectives on the use of different CGM systems is still lacking, especially on recent tools developed by new technologies.

Study Objectives

Primary objective

Assessment of Pre-set targeted time in hypoglycemia and number of episodes of pre-set hypoglycemia during the different periods of use of CGM tools based on different alarms.

Secondary objectives

Accuracy of the two different CGM systems (comparator SBGM by capillary finger stick).

Assessment of patients' perspectives and tolerance to the use of two subsequent different CGM systems and tools, in particular on different types of alarms: Dexcom One Plus (Dexcom) with threshold alarm and Dexcom G7 (Dexcom) with predictive alarm.

Assessment of quality of life and sleep quality.

Assessment and comparison of glycemic control, patients' perspective and tolerance of CGM with USUAL Care CGM.

Study Design

Study Type

Prospective interventional with medical devices CE

Study Site

Sample Size Estimation

11 IMDs at risk for hypoglycemia

The rare condition of disorders investigated needs to be considered for the sample size (e.g. GSD I has a frequency of approximately 1 in 100,000 and the estimated incidence of CHI ranges between 1:27,000 and 1:50,000 live births in outbred western population).

Randomization

Patients will be randomized to start with the use of Dexcom G7 o Dexcom One Plus after baseline.

Methods for randomization: Randomization will be employed to assign participants to different

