Statistical Analysis (example)

(1) General Principles

Quantitative variable will be described by the total number of cases, number of missing values, mean, and standard deviation, minimum, maximum and median. Categorical variables will be described by the number of cases and percentages.

All statistical tests will be performed using two-sided test, P value less than or equal to 0.05 will be considered to have examined the difference statistically significant (Unless otherwise noted). For comparison between two groups of the general condition, the suitable method shall be adopted to conduct analysis according to the type of indicators; for the comparison among groups of quantitative data, group t test (homogeneity of variance, normal distribution) or Wilcoxon rank-sum test will be adopted according to the data distribution (the Shapiro-Wilk test will be used beforehand to check whether the variables follow a normal distribution or not); for categorical data, the chi-square test or Fisher's exact test (if the chi-square test is not applicable) shall be adopted; for ordered data, Wilcoxon rank-sum test or Cochran-Mantel-Hansel test shall be adopted. Multiple regression analyses will also be considered, including linear regression for continuous dependent variables, Poisson regression and cumulative logit logistic regression for ordered response variables (or logistic regression for dichotomous variables, such as presence/absence). Moreover, ANOVA or mixed-effects models will be used to compare how the effect of interest varies over time within the same subject, repeated measures.

(2) Completion and Baseline Parameters

The summary of the study completion includes the count of completed cases of each study center, the list of dropout cases, the analysis set description, the comparison of dropout rates of the groups and the list of reasons for incompleteness. The summary of baseline parameters includes demographic characteristics (gender, age, height, vital signs etc.), history of illness and medications, and specific Questionnaires about CGM tolerance, perspectives and expectations. Comparisons among the two different CGM devices groups and gold standard by capillary finger stick will be conducted to evaluate MARD and reliability during the period of observation.

(3) Compliance

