- Compliance of study: study compliance to the CGM two medical devices and capillary finger sticks of all groups will be described and compared. A list of subjects with poor compliance (80% below or 120% above compliance) will be generated.

Observation parameters list (CRF)

Patients at screening, baseline, after 30 days of **unblinded monitoring** with Dexcom G7 and 30 days of **unblinded monitoring** with Dexcom One Plus (Fig. 2). The start of the single CGM tool will be randomized (i.e. 50% of patients will random start with G7 and then switch to Dexcom One Plus, and *viceversa*).

- 1) SCREENING _ General data collection: age, gender, height, body weight, minority, career, income, degree of education, family history, smoking habit, primary diseases or accompanied diseases.
- 2) SCREENING _ Previous glucose monitoring (referring to the last 8 weeks): number of capillary fingers sticks per day, use (or not) of CGM and type of CGM device
- 3) SCREENING _ Major comorbidities
- 4) SCREENING _ Document intake of medications
- 5) SCREENING _ Adverse events and the rate of hospitalization during the last year
- 6) BASELINE _ Quality of Life (SF-12 rating scale)
- 7) BASELINE _ Quality of Sleep (Pittsburgh sleep quality index (PSQI))
- 8) FOLLOW UP _ Capillary finger sticks glucose values (3 per day) by diary record

- 9) FOLLOW UP_ CGM values: time above, under or in the pre-set target, number of episodes of pre-set hypoglycemia
- 10) FOLLOW UP_ CGM tolerance, perspectives and expectations (Specific questionnaires)
- 11) FOLLOW UP_ CGM Quality of Sleep (Pittsburgh sleep quality index (PSQI), quality of life (SF12))
- 12) FOLLOW-UP_ Education on the use of CGM device (sensor, receiver or other tools)

Flowchart indicating which parameter is measured when:

Observation Parameters	Screening	Enrollment/Baseline	Follow up - After 30 days	Final Visit study - After 30 days
Informed consent	x			
Demographic (Age, Gender, Career, Degree of Education, Income)	x			
Height	x			
Body Weight	x	x	x	x
Family History	x			
Smoking Habit	x			
Physical exam	x			
Vital signs	x			
Primary Diseases or Accompanied Diseases	x			
Major IMD Comorbidities	x			
Glucometer values		x	x	x
Use of CGM	x			
Documented Intake of Medications	x			
Rate of Hospitalization During the Last Year	x			
Type of CGM Device	x	x	x	x
Capillary finger sticks glucose values (3 per day)		x	x	x
CGM values (time in pre-set hypoglycemia, number of pre-set hypoglycemia, MARD)		x	x	x

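### The only tests the plan ties to quantitative comparisons are unpaired and picked by a normality pre-test, although the device contrast in this 11-patient crossover is within-patient

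*Combined protocol and SAP*

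**What the plan says.** All references are to the combined protocol and SAP.

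- **Selection rule** (Statistical Analysis, (1) General Principles). The rule applies "for the comparison among groups of quantitative data". There, a "group t test (homogeneity of variance, normal distribution) or Wilcoxon rank-sum test will be adopted according to the data distribution", and "the Shapiro-Wilk test will be used beforehand to check whether the variables follow a normal distribution or not". Both tests are for independent groups. The paragraph names no paired t test or signed-rank test and does not mention differences or residuals.
- **Within-subject methods** (same paragraph). "ANOVA or mixed-effects models will be used to compare how the effect of interest varies over time within the same subject". Linear and Poisson regression are also to be considered. No sentence assigns any of these to an endpoint.
- **Design** (Sample Size Estimation; Observation parameters list). The sample is "11 IMDs at risk for hypoglycemia". Order is randomized: "50% of patients will random start with G7 and then switch to Dexcom One Plus", and the rest go the other way.
- **Primary endpoints** (Endpoints). Hypoglycemia episode counts, time above, below and in range, and glycemic variation are compared between device periods. All are quantitative.
- **Error rate** (General Principles). "All statistical tests will be performed using two-sided test", and a "P value less than or equal to 0.05 will be considered to have examined the difference statistically significant".

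**The concern.** The same patients supply the values under both devices. An independent-groups test puts the spread between patients into the error term, although that spread cancels from the device contrast. Patients with different glycogen storage disorders or hyperinsulinism are likely to differ widely in their usual number of episodes, so the error term could be much too large.

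The paragraph offers two routes for the same primary comparison, an unpaired test selected by the data or a repeated-measures model, and does not say which applies. An analyst who follows the first route to the letter could miss a real difference between threshold and predictive alarms.

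The Shapiro-Wilk step adds a smaller problem. For a paired contrast, normality matters for the differences or residuals, not for the variables themselves. Letting the step choose between a test of means and a test of ranks also means that what is being estimated is settled only after the data are seen.

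**Working it through.** **The plan's own figure.** The sample size of 11 comes with no effect size, SD, within-patient correlation or power, so there is nothing to reproduce. Distributions, correlations and effects below are assumptions, shown over a range.

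**1. What ignoring the pairing does.** With n patients, SD σ under each device and within-patient correlation ρ:

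- true variance of the mean difference = 2σ²(1−ρ)/n
- variance used by the unpaired test = 2σ²/n
- ratio of standard errors = 1/√(1−ρ)

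At ρ = 0.5 the unpaired standard error is 1/√0.5 = 1.41 times too large. At ρ = 0.8 it is 1/√0.2 = 2.24 times too large.

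Simulated rejection rates for 11 patients with normal data, two-sided 0.05 (20,000 runs):

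| ρ | No effect: unpaired / paired t | True difference 0.5 SD: unpaired / paired t |
|---|---|---|
| 0 | 4.8% / 4.7% | 20% / 19% |
| 0.3 | 2.2% / 5.1% | 17% / 25% |
| 0.5 | 0.8% / 4.8% | 13% / 32% |
| 0.7 | 0.2% / 5.0% | 10% / 49% |
| 0.8 | 0.03% / 4.9% | 7% / 66% |

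**2. Skewed episode counts.** Assumed model: patient rates gamma with shape 1 and mean 12 episodes per 30 days, and within-patient variation gamma with shape 6. The stated rule is read as Shapiro-Wilk on the 11 values under each device, then the t test if neither rejects and the rank-sum test otherwise. Results from 2,000 trials:

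| Analysis | True halving | No effect |
|---|---|---|
| Stated rule (pre-test, unpaired tests) | 11% | 0% |
| Same pre-test on raw values, but paired tests | 58% | 4% |
| Paired log ratio, no pre-test | 54% | 4% |

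Simulation error at 54% is √(0.54 × 0.46/2,000) = 1.1 percentage points. Going from row 1 to row 2 changes only the pairing and recovers the whole gap. A separate 3,000-trial run shows the same from the other side. With unpaired tests and a true halving, the pre-test rule rejects in 12.9%, a fixed t test in 12.2% and a fixed rank-sum test in 9.9%.

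**3. A different shape.** With lognormal data (log-SD 0.7) and a shift of 0.5 SD on the log scale, the stated rule has 9% power against 55% for the signed-rank test at ρ = 0.8, and 15% against 26% at ρ = 0.5 (2,500 runs).

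**4. What the pre-test detects at n = 11** (6,000 runs per shape):

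- moderate skew: 16% (gamma, skewness 1), 28% (gamma, skewness 1.4), 29% (lognormal, log-SD 0.5)
- strong skew: 51% (exponential), 67% (lognormal, log-SD 1)
- in the count model of step 2, at least one device period is flagged in about 80% of trials

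**5. Whether it looks at the right distribution** (two constructed cases, n = 11):

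- skewed patient levels, normal differences: the check on the variables rejects in at least one period in 44% of trials, the check on differences in 5%
- normal patient levels, skewed differences: 11% and 24%

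**6. Whether the choice of test matters once the tests are paired.** In the count model under a halving, the paired t and signed-rank tests disagree on significance in about 19% of trials.

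**The case against.** Three objections carry weight.

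**Scope.** The sentence containing the rule opens by referring to the general condition of the two groups, so it may be aimed mainly at baseline comparisons. Categorical and ordered data have their own tests. A reader might infer that the pre-test governs every outcome, but the text does not say so. What stands is that the primary endpoints are quantitative, nothing exempts them from the rule, and nothing sends them elsewhere.

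**Suitable models are already named.** A reader might infer that the plan contains no within-subject method. It does: ANOVA or mixed-effects models, in the same paragraph. Used for the device contrast, they would respect the pairing. The defect is that they are attached to no endpoint, which leaves two competing routes.

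**The pre-test does little measurable harm.** A reader might infer that it causes the loss of power, or that at this sample size it usually misses skewness. Neither is supported. The same raw-value check followed by paired tests performs as well as the fixed log ratio, with type I error at 4%. Strong skew is detected in half to two thirds of samples. The much lower detection rates at 5 or 6 patients per sequence do not describe the device comparison, which has 11 values under each device. Also, for the unpaired tests actually listed, normality of the variables within each group is the relevant assumption. The check becomes the wrong one only once the comparison is recognised as paired.

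**Conclusion.** The point holds in this form: the primary device comparison has no fixed within-patient analysis, and the only tests the plan assigns to quantitative group comparisons are unpaired. If those tests are used, intervals are too wide and the tests too conservative whenever a patient's two periods are positively correlated. Under the assumed skewed counts and a true halving, power is about 11% instead of about 54%, and the false-positive rate is about 0% instead of 4%. The size depends on the correlation, which the documents do not give. At ρ = 0 there is essentially no loss, and at ρ = 0.5 to 0.8 the loss is large.

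The Shapiro-Wilk step is a secondary fault of interpretability. It examines a distribution that does not bear on the paired contrast, and it leaves the effect scale (mean difference or rank shift) open until the data are in. With about 19% disagreement between the candidate paired tests, that choice can decide the conclusion. It should not be credited with any of the power gap.

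**What to change.** For the primary device comparison, replace the Shapiro-Wilk-selected group tests with one pre-specified within-patient analysis per endpoint, each with a period term.

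- **Episode counts (each threshold):** within-patient log rate ratio, with a stated rule for zero counts such as adding 0.5. Zeros will matter. Under the assumed rates, taking counts as Poisson and ignoring within-patient variation, a patient's chance of none in 30 days is 1/(1+12) = 1/13. The chance that at least one of 11 patients has none is then 1 − (12/13)¹¹ = 59%. If the mean is halved to 6, it is 1 − (6/7)¹¹ = 82%.
- **Time in ranges and glycemic variation:** within-patient difference.
- **Sensitivity analysis:** a re-randomization test that respects the sequence allocation actually used. A fixed 6/5 split gives 462 possible allocations, enough for a test at 0.05.
- **Normality:** examine differences or residuals descriptively only. Do not use the result to select a test.

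If the group tests are meant only for baseline comparisons, say so.

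A mixed negative-binomial model is an alternative for the counts, but it may be unstable with 11 patients.

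The change is one of wording. Its cost is a commitment to one effect scale per endpoint and one degree of freedom for period. Residual degrees of freedom fall from 10 to 9, so the t multiplier rises from 2.228 to 2.262, about 1.5%.

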Continuous Glucose Monitoring (CGM) systems to ensure unbiased comparisons across the study groups. Simple randomization using computer-generated random numbers will be implemented to allocate patients randomly. This method will help distribute confounding variables evenly between groups, thereby minimizing selection bias. Block randomization may also be utilized to maintain balance in the number of participants among the groups throughout the study. Allocation concealment will be maintained until the intervention assignment to prevent any potential influence on patient enrollment.

Statistical method

Definition of Analysis Sets

The following data sets will be analyzed:

- Full analysis set (FAS):
The set of subjects is as close as possible to the ideal implied by the intention-to-treat principle. All subjects with at least one efficacy follow-up will be included. It is derived from the set of all eligible subjects by minimal and justified elimination of subjects. When handling of missing values of primary outcomes, the last observation carried forward (LOCF) method will be applied.
- Per-protocol analysis set (PPS):
The per protocol analysis set will consist of all patients in the full analysis set plus the following criteria: completion the treatment process, without any major protocol violations, good compliance (80%~120% medical device and capillary finger sticks compliance) and without missing value in primary outcomes. Patients with at least one major protocol violation (e.g missing the 8 weeks efficacy follow up) will be excluded from the per-protocol analysis.
- Safety Set (SS):
The safety set will consist of all subjects followed at least one period with one CGM system.

Endpoints:

Primary: number of episodes of pre-set hypoglycemia (hypoglycemia <70 mg/dL and severe hypoglycemia < 54 mg/dL), time above, under or in pre-set target range, glycemic variations during the different periods of use of CGM tools based on different alarms;

Secondary objectives

Secondary: accuracy and MARD (comparator finger capillary sticks) during the use of two different CGM; perspectives and preferences in monitoring and specific use of different alarms with Dexcom One Plus or with Dexcom G7; correlation of primary endpoint with the quality of sleep, quality of life and/or neurocognitive outcomes i.e. attention, assessed by specific questionnaires; perspectives and preferences in monitoring and specific use of different CGM with Usual Care monitoring.

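### The primary hypoglycemia endpoint counts episodes without dividing by the time the sensor was recording, so unequal recording on the two devices biases the comparison in either direction

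*Combined protocol and SAP*

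**What the plan says.** The Endpoints section opens the primary endpoint with "number of episodes of pre-set hypoglycemia (hypoglycemia <70 mg/dL and severe hypoglycemia < 54 mg/dL". The primary objective, the CRF list and the flowchart also speak of a number of episodes. No rate, exposure time, offset or minimum recording time appears anywhere.

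The design is a two-period crossover of 30 days per device, in which "50% of patients will random start with G7 and then switch to Dexcom One Plus" and the rest take the reverse order. The sample size is given as "11 IMDs at risk for hypoglycemia".

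Adherence enters in two places. The per-protocol set requires "good compliance (80%~120% medical device and capillary finger sticks compliance", and the Compliance paragraph says that compliance will be described, compared and listed when poor. Neither adjusts the episode counts. The full analysis set needs only one efficacy follow-up.

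General Principles names an unpaired t test or rank-sum test for quantitative data, and ANOVA or mixed models for repeated measures within a subject. Among regressions that may also be considered it lists "Poisson regression and cumulative logit logistic regression for ordered response variables". No distribution, link, offset or dispersion term is given for any of these.

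**The concern.** A sensor cannot register an episode while it is not recording. The device that records less therefore appears to prevent more hypoglycemia. Randomising the order of devices does not remove this if recording time depends on the device. Such dependence is plausible here, because tolerance of the two alarm types is itself a secondary objective.

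The second, smaller issue is that a Poisson model takes the variance as equal to the mean. If a patient's underlying rate differs between the two periods for reasons unrelated to the device, the Poisson standard error is too small, even with patient effects in the model. Poisson is also a model for counts, so attaching it to ordered responses is a wording error.

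At stake is one of the headline comparisons of the trial: a false difference between devices, or a real one missed.

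**Working it through.** **Inputs from the documents.** 11 patients, each using both devices; 30 days per device; two-sided tests with "P value less than or equal to 0.05 will be considered" significant; the compliance band of 80–120%. The plan states no episode rate, variance, effect size or power, so there is no figure of its own to reproduce.

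**Assumptions, not from the documents.** Mean of 2, 5, 15 or 30 episodes per period; recorded time of 80% against 100%; gamma-distributed patient rates with relative variance v (0.5 unless stated); a within-patient period-to-period CV, c, of 0 to 50%.

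**Step 1: recording time.** Expected count = true rate × recorded time, so the count ratio B/A = (rate B × time B) / (rate A × time A).

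- Equal rates, A records 30 days and B records 0.80 × 30 = 24 days: ratio = 24/30 = 0.80. With the devices exchanged, 30/24 = 1.25.
- True rate ratio 0.80, with the higher-rate device A recording 80%: ratio = (0.80 × 30)/(1 × 24) = 1.00. The difference disappears.

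This is a bias in the quantity being estimated, so it does not depend on the test.

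**Step 2: what the listed tests make of it** (simulated trials of 11 patients, equal true rates, 80% against 100% recorded time).

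- Paired t test on raw counts: false rejection of 15% at 5 episodes rising to 59% at 30 when c = 0, and 10% rising to 19% when c = 30%.
- Poisson, c = 0, v = 1: 20%, 47% and 75% at 5, 15 and 30 episodes.
- The same paired test on rates per recorded time: about 5%.
- Unpaired t or rank-sum test, v = 1: rejection stays near zero, because these tests discard the pairing. The ratio is still biased. With equal wear they also reject in under 1% of trials when the true ratio is 0.80.

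In the hidden-effect case, tests on raw counts reject in about 5% of trials. A paired test on recorded-time rates rejects in 11%, 27% and 46% at 5, 15 and 30 episodes (v = 1, c = 0).

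**Step 3: Poisson, if it were used** (equal recording, no device effect). The variance of the pooled count is inflated by φ = 1 + c² × mean × (1 + v), and the approximate size of the test is 2 × [1 − Φ(1.96/√φ)]. For mean 15 and c = 30%: φ = 1 + 0.09 × 15 × 1.5 = 3.03, 1.96/√3.03 = 1.13, size ≈ 26%. Simulation gives 24%.

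| Mean episodes | c = 20% | c = 30% | c = 50% |
|---|---|---|---|
| 15 (simulated) | 15% | 24% | 43% |
| 30 (simulated) | 23% | 37% | 56% |
| 2 (formula) | 6% | 8% | 14% |

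Simulation at a mean of 2 gives about 7–14%, and 6–16% over v from 0.25 to 1. With c = 0 the size is 5% whatever the spread between patients, so only variation within a patient matters.

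**Step 4: candidate remedies at n = 11.** A paired t test on log counts holds 4–5%. Quasi-Poisson leaves about 5.5–15%. Negative binomial with patient fixed effects gave about 11%, 18% and 22% at mean 15 for c = 20%, 30% and 50% (400 runs per case, so approximate).

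**The case against.** A reader might infer that the plan commits to Poisson and that its p-value will therefore overstate the evidence. The documents do not support that. Regressions are only to be considered, Poisson is not tied to the episode endpoint, and the section is headed as an example. The firm wording names t or rank-sum tests and ANOVA or mixed models. Extra-Poisson variation does not inflate those: a paired t test on raw counts holds 4–5% when recording is equal. This objection stands, and it makes the Poisson point conditional.

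A reader might also take the 80% compliance limit to mean 80% wear. It is not defined that way. It covers the device and finger sticks together, and it has a 120% ceiling that continuous wear could not reach. The 0.80 ratio is thus a scenario, and it needs a systematic difference between devices. Both come from one manufacturer and have the same nominal period, so the actual gap may be smaller. Compliance is to be compared between devices, so an imbalance might be noticed.

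These arguments limit the size of the wear problem without removing it. Noticing an imbalance does not correct the counts, the full analysis set has no limit at all, and no listed method adjusts for recording time.

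**Conclusion.** The missing exposure denominator is a real fault and does not depend on the choice of test. The count ratio moves in direct proportion to the ratio of recorded time, in either direction. How far it will move in this trial cannot be told from the documents.

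The Poisson point holds only if that model is chosen for episodes and only if rates vary within a patient between periods. Its size rests wholly on assumed CVs and means, and is modest when episodes are few, as may be so for the lower threshold. The wording that attaches Poisson to ordered responses is wrong in any case.

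The change should be made before the data are analysed. It concerns the validity of a primary comparison, not safety or trial conduct.

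**What to change.** - Define the endpoint, at each threshold, as episodes per recorded sensor-day for each patient and device period.
- Make the primary analysis a patient-level paired crossover analysis of log rates, with device and period effects and a small continuity correction for zero counts (for example 0.5). Report the rate ratio with a t-based 95% CI.
- Do not use plain Poisson for episodes, and do not rely on quasi-Poisson or negative binomial alone with 11 patients.
- Correct the sentence that lists Poisson as a method for ordered responses.

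The cost is mostly wording. Recorded sensor time must be extracted for each device period and, as the CRF list has no such item, added to the CRF if it is not already captured. No extra patients or visits are needed. The episode comparison may look less favourable than one on raw counts.

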STUDY PROTOCOL (version 2 - 17/09/2024)

Study Title:

The efficacy of different Continuous Glucose Monitoring systems in a cohort of adult patients affected by Inherited Metabolic Disorders prone to Hypoglycemia

Study Type:

Interventional study with CE-marked medical device, single-center, spontaneous

Sponsor:

University Hospital of Padova

Principal Investigator:

[name], MD, PhD

[contact]

Email: [contact]

Coordinating Center:

Division of Metabolic Diseases

Director: [name]

University Hospital of Padova

[name]

Study Background	5
Study Objectives	6
Primary objective	6
Secondary objectives	6
Study Design	6
Study Type	6
Study Site	7
Sample Size Estimation	7
Randomization	7
Statistical method	7
Definition of Analysis Sets	7
Endpoints:	7
Statistical Analysis (example)	8
Observation parameters list (CRF)	8
Study Duration	10
Schematic Study Plan	10
Figure 2. Time design of the study (arrows correspond to a sensor change or a device/system switch)	11
Study Population	11
Inclusion Criteria	11
Exclusion Criteria	11
Study Evaluation	11
Study Quality Control	11
Requirements of Ethics	12
Management Principles	12
Resume	12
Record Storage in the Study Site	12
Protocol Revision	12
Termination of Study Protocol	12
References	13

Abbreviations (examples/alphabetical order)

Abbreviation	Definition
CGM:	continuous glucose monitoring;
CH:	congenital hyperinsulinisms;
FGM:	flash glucose monitoring;
GSD:	glycogen storage disorders;
GV:	glycemic variation;
IMD:	inherited metabolic disorders;
MARD:	mean absolute relative difference;
Rt-CGM:	real time continuous glucose monitoring;
SMBG:	self-monitoring blood glucose;
TAR:	time above range;
TIR:	time in range;
T1DM:	type 1 diabetes mellitus;

Trial Title	The use of Continuous Glucose Monitoring in Inherited Metabolic Disorders prone to Hypoglycemia: Patients' Perspectives and Reliability between Different Devices from an Observational Study
Principal Investigator	[name]
Study Objective/research question	Assessment of perspectives and glycemic reliability of different real time CGM devices in a cohort of adult IMDs patients prone to hypoglycemia
Study Design	Prospective interventional with medical devices CE

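### Sensor agreement with finger sticks is left to unpaired difference tests: MARD is named, but no agreement analysis, interval or unit of analysis is given

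*Combined protocol and SAP*

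**What the plan says.** The synopsis gives as the study objective "Assessment of perspectives and glycemic reliability of different real time CGM devices". Accuracy against capillary finger sticks is a secondary objective, and accuracy with MARD is a secondary endpoint.

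The one analysis sentence for this is in Statistical Analysis (example), part (2) Completion and Baseline Parameters: "Comparisons among the two different CGM devices groups and gold standard by capillary finger stick will be conducted to evaluate MARD and reliability". It treats the finger stick as one of the things compared, and it lists reliability beside MARD without defining it.

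Part (1) General Principles supplies the tests: "for the comparison among groups of quantitative data, group t test (homogeneity of variance, normal distribution) or Wilcoxon rank-sum test will be adopted", with the choice depending on a Shapiro-Wilk check. It adds "All statistical tests will be performed using two-sided test" and "P value less than or equal to 0.05 will be considered to have examined the difference statistically significant". Regression models are also mentioned. ANOVA or mixed-effects models are mentioned for how an effect changes over time within a subject, with no link to accuracy.

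The plan does not mention limits of agreement, a confidence interval for MARD, or whether the unit of analysis is the reading or the patient.

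The design is a crossover: "50% of patients will random start with G7 and then switch to Dexcom One Plus", and vice versa. The sample size section gives "11 IMDs at risk for hypoglycemia".

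**The concern.** Reliability against a reference is a question about the size of individual errors. A t test or rank-sum test of sensor values against finger-stick values asks whether the two sets have the same average or the same ranks. Positive and negative errors cancel in that comparison, so a non-significant result says little about agreement. A significant result may reflect only a small constant offset. The answer also depends on whether readings or patient means are tested.

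For device against device, every patient wears both sensors. An unpaired test ignores this and gives away precision that 11 patients can ill afford.

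The stakes go beyond a secondary endpoint. The primary endpoints are episodes below 70 and 54 mg/dL and times in range, and all are read from these sensors. A loosely supported statement that the sensors are reliable, or equally accurate, would be used to support those results.

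**Working it through.** The plan gives no accuracy calculation to reproduce. The check asks what the listed tests would do with the data the plan schedules.

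**Inputs from the documents.** 11 patients; 3 finger sticks per day; 30 days per device; two-sided 0.05. Pairs per device are at most 11 × 3 × 30 = 990, or 90 per patient.

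**Assumptions (not in the documents).** Mean glucose 100 mg/dL, between-patient SD 12, within-patient SD 25. Relative error = bias + patient effect + residual.
- Noisy sensor: bias 0, patient SD 5%, residual SD 25%. Total SD = √(5² + 25²) = 25.5%, so MARD = 25.5 × √(2/π) = 20.3%.
- Offset sensor: bias +3%, patient SD 3%, residual SD 9%. Total SD = √(3² + 9²) = 9.5%, with MARD 7.9%.

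**Noisy sensor, patient means.** The variance of a finger-stick patient mean is 12² + 25²/90 = 151. For the sensor it is about 151 + 25 + 7.5 = 184. The unpaired standard error is √((151 + 184)/11) = 5.5, so significance needs a difference of about 2.086 × 5.5 = 11.5 mg/dL. The actual mean difference varies around 0 with SD √((25 + 7.5)/11) = 1.7. The listed test therefore flags it in about 0% of trials. A paired or one-sample test on patient means flags it in about 5%, which is just the test's error rate when the mean bias is zero (5.0% and 5.5% in two simulations).

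**Offset sensor, same data, two units.** The true mean difference is 3 mg/dL, and its SD is about √((9.1 + 1.0)/11) = 0.96.
- Patient means, listed t test: standard error √((151 + 170)/11) = 5.4, threshold 2.086 × 5.4 = 11.3 mg/dL. Flagged in about 0% (simulated 0–0.7% for between-patient SD 8–15).
- Pooled readings, listed t test: variances 12² + 25² = 769 and about 913, standard error √((769 + 913)/990) = 1.30, threshold 1.96 × 1.30 = 2.55 mg/dL. The chance of exceeding it is Φ((3 − 2.55)/0.96) = Φ(0.47) = 68% (simulated 70–71%).

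The noisy-sensor result is claimed for patient means only. Pooling ignores clustering. Repeating this error model on pooled readings (2,000 runs each for between-patient SD 8, 12 and 15) flagged the noisy sensor in about 10% by t test and about a third by rank-sum test. That again shows dependence on unit and test.

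**Agreement estimates on the same sensors.** Approximate 95% limits of agreement:
- Noisy: 0 ± 1.96 × 25.5 = −50% to +50%.
- Offset: 3 ± 1.96 × 9.5 = about −16% to +22%.

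These separate the two sensors directly.

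**Device against device.** With SD σ and within-patient correlation ρ, the variance of the mean difference is 2σ²/n unpaired and 2σ²(1 − ρ)/n paired. Power at 0.5 SD with n = 11 is 20.1% unpaired (11 against 11) and 32.3% paired (0.5 SD of the within-patient differences). These describe the same raw difference when ρ = 0.5. The chance of missing it is then about 80% and 68%. The 0.5 SD is illustrative and not tied to any particular MARD difference.

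**The case against.** The strongest defence is that MARD is named in the analysis sentence itself, in the endpoints and in the flowchart. MARD averages absolute errors, so they cannot cancel. The noisy and offset sensors above would be reported with MARD of about 20% and 8% and ranked correctly. A test on patient-level MARDs would also detect a gross difference between devices: with error SD 25 against 10 mg/dL, simulated power was about 1.00, paired or unpaired, with 11 patients. All of this stands.

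A reader might infer that under this plan a noisy unbiased sensor would be declared reliable and a precise one with a small offset rejected. The documents do not support that. No sentence makes non-significance the criterion for reliability or significance the criterion against it, and part (2) names no test. The offset half is also conditional. The listed unpaired test on patient means almost never flags a +3% offset; frequent flagging requires pooled readings, or a paired or one-sample test that the plan does not list for this purpose.

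It can also be said that mixed models are available and could respect the crossover. They could, but the plan ties them to change over time and not to accuracy or the device comparison. Finally, accuracy is secondary, and a small rare-disease study cannot be expected to prove equivalence. That is fair, and it is why a margin is not required here.

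**Conclusion.** The concern holds as an omission. The plan names MARD, but its only stated rule for comparing quantitative data between the devices and the finger stick is an unpaired difference test, which cannot show agreement. On patient means, an unbiased sensor with MARD of about 20% would be flagged in 0–5% of trials. A +3% offset would be flagged in about 0% or about 70%, depending on a unit of analysis that the plan leaves open. The unpaired test also wastes the within-patient comparison of devices.

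The percentages rest on assumed glucose levels and error sizes. The qualitative point does not: a test of equal averages is not a test of agreement. The plan contains no pass/fail rule, so the finding is that a conclusion on reliability would lack a basis, and not that the plan forces a wrong one.

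**What to change.** In part (2), replace the difference test against finger sticks with estimation:
- For each device, report MARD and repeated-measures 95% limits of agreement, with 95% CIs clustered by patient. This settles the unit: paired readings within patients. State how a sensor value is matched in time to a finger stick.
- Compare the devices by the within-patient difference in MARD with its 95% CI.
- State that p>0.05 is not evidence of reliability or of equal accuracy.

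An equivalence margin is optional. Without one, report the device comparison as estimation only and draw no conclusion of similarity.

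The cost is analysis wording and slightly more analysis work. The three daily finger sticks and the CGM values are already scheduled. The downside is that with 11 patients the intervals may be wide and the device comparison inconclusive.
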